Proprietary confidential information © 2019 Boehringer Ingelheim International GmbH or one or more of its affiliated companies

Trial period								Residual Effect Period (REP)		Extended Follow-up
Visit	Cycles ≥ 4					Cycles >7	REP		Follow-up	
	1	2	3	4 or End of Cycle	1	End of Treatment	End of REP	FU*****		
Day(s) in respective treatment cycle**)	1	2-5	8	15	22	29±3****	1	As soon as possible but not later than one week after permanent discontinuation of trial medication(s)	Not earlier than 30 days after last infusion with trial medication(s)	every 12 weeks ± 2 weeks**** (No FU visits after approval of CTP version 7.0)
DISEASE ASSESSMENT										
Disease assessment with peripheral blood and clinical assessment						x	x ¹⁹	x ¹⁹		
Disease assessment with BM aspirate (and biopsy if indicated) Separate portion of BM samples for biomarkers ¹¹ (see Table 3 and Table 4)						x ¹²	x ¹⁹	x ^{11, 13, 19}		
Cytogenetics and molecular genetics ¹⁴										
TRIAL MEDICATION										
Administration of decitabine intensive treatment (starting in Cycle 1 with treatment on 10 consecutive days)	x	x								
Administration of decitabine standard treatment (starting in Cycle 1 with treatment on 5 consecutive days)	x	x					x			
Administration of premedication ¹⁷	x		x	x	x		x			
Administration of BI 836858 ^{17, 18} (for details on BI 836858 administration refer to Table 4.1.3.1:2 and 4.1.3.2:1)	x		x	x	x		x			
Eligibility check for (further) drug administration of BI 836858	x		x		x	x	x			

Trial Protocol

Proprietary confidential information © 2019 Boehringer Ingelheim International GmbH or one or more of its affiliated companies

- *) The planned duration of a treatment cycle is 28 days. Day 1 of each cycle is defined as the day when the first dose of decitabine in that cycle is administered. The start of the next cycle must not be earlier than Day 29 of the previous cycle. There will be a maximum of 4 administrations of BI 836858 in one treatment cycle (with the exception of treatment Cycle 1, where there is a maximum of 3 administrations of BI 836858). All assessments should be performed prior to dose administration on dosing days, unless otherwise specified.
- **) Days are calculated as calendar days. Please refer to [Section 6.2](#) for details on time windows for visits and individual study procedures or assessments.

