6.7 BASELINE, TIME WINDOWS AND CALCULATED VISITS

Study days and visits will be labelled according to the CTP's flow chart.

Unless otherwise specified, baseline is defined as the time-point closest to but prior to first administration of trial medication in course 1. Note that for some trial procedures (for example body weight, vital signs, laboratory tests) this may be the value measured on the same day trial medication was started. In these cases it will be assumed that the

measurements were taken according to protocol, i.e. prior to first intake of any trial medication.

Laboratory values: Baseline is defined as the latest time-point before the very first administration of any trial medication in course 1. For laboratories where not only the examination date but also time are recorded, examination time has to be taken into account when defining baseline. That is, a laboratory value on the same date as the first trial drug administration is considered as baseline value if and only if the time of laboratory value is before or the same as the time of first trial drug administration.

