7.8.2 Laboratory data

The analyses of laboratory data will be descriptive in nature and will be based on BI standards (9). It will include a graphical summary highlighting potential cases of Hy's Law.

The analysis of laboratory data will use the same 'analysing treatments' as described for the AEs, except for that the baseline laboratory value will be included in the 'on-treatment period'. Subjects having at least one post-baseline laboratory value will be displayed in the descriptive analyses. The following parameters are of particular interest:

- haematology: haemoglobin, white blood cell count, Absolute Neutrophil Counts, platelets
- Biochemistry: aspartate transferase, alanine transferase, bilirubin, serum creatinine, urea, sodium, potassium, magnesium
- Coagulation: international normalised ratio, partial thromboplastin time

Laboratory values: Baseline is defined as the latest time-point before the very first administration of study medication. A laboratory value on the same date as the first study drug administration is considered as according to protocol, i.e. as prior to first study drug administration and will therefore be used as baseline value.

The following outputs will be presented:

- Worst CTCAE grade experienced during the on-treatment phase.
- Transitions of CTCAE grade from baseline to worst laboratory value, from worst to last laboratory value on treatment and from baseline to last laboratory value during the on-treatment phase.

Worst laboratory value and its CTCAE grade (highest CTCAE grade) over all courses will be calculated for each laboratory parameter specified above.

The last laboratory value on treatment is the laboratory value of the last visit of the last course of each subject.

Furthermore, a summary table of possible clinically significant abnormalities will be given.

Possible clinically significant abnormal laboratory values are defined as those laboratory values that are of CTCAE grade ≥ 2 and show an increase from baseline value by at least one CTCAE grade. Frequency of subjects with possible clinically significant abnormal laboratory values will be provided whenever applicable. If no baseline value is available but the subject has a post-baseline laboratory value of CTCAE grade ≥ 2 an increase from baseline will be assumed, i.e. the laboratory value considered as possible clinically significant.

Hepatic injury:

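### SAP 6.7 and 7.8.2 conflict on whether a laboratory sample timed after the first dose, on the same day, can serve as baseline

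*SAP*

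**What the plan says.** SAP section 6.7 (Baseline, time windows and calculated visits) has two layers. Its general paragraph applies unless something else is specified. It allows baseline to be measured on the day treatment starts, names laboratory tests among its examples, and assumes that such "measurements were taken according to protocol, i.e. prior to first intake of any trial medication". A separate laboratory paragraph then refines this: "For laboratories where not only the examination date but also time are recorded, examination time has to be taken into account when defining baseline". A value from the day of first dosing counts "if and only if the time of laboratory value is before or the same as the time of first trial drug administration".

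SAP section 7.8.2 (Laboratory data) defines the laboratory baseline again. It opens in line with 6.7: "Baseline is defined as the latest time-point before the very first administration of study medication". The next sentence takes a different line: "A laboratory value on the same date as the first study drug administration is considered as according to protocol". Every such value is thus presumed to be pre-dose and becomes the baseline. This sentence has no time check and is not limited to samples without a recorded time. Neither section refers to the other or says which prevails.

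The protocol's default order, in the Flow Chart footnotes, is sampling before dosing: "All assessments should be performed prior to dose administration on dosing days, unless otherwise specified".

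**The concern.** A strict condition in one section and an unconditional rule in the other cannot both hold for a sample known to have been drawn after the first dose. If 7.8.2 is followed literally, that sample becomes the baseline. Where a true pre-dose value also exists, the post-dose value displaces it, because the latest qualifying time-point is taken.

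Baseline matters in 7.8.2 because two of its three CTCAE transitions start from it, and because a possible clinically significant abnormality needs grade 2 or higher together with a rise of at least one grade from baseline. If such samples exist, the SAP does not tell the programmer which value to use, and the two sections can lead to different entries in these tables.

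**Working it through.** There is no figure to reproduce. The check is to apply each rule to every kind of laboratory value that can fall on the date of first dosing.

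| Sample on the date of first dosing | SAP 6.7 | SAP 7.8.2 | Agree? |
|---|---|---|---|
| Timed, at or before the dose | Baseline | Baseline | Yes |
| Date only, no time | Assumed pre-dose, so baseline | Baseline | Yes |
| Timed, after the dose | Not baseline; the last earlier value is used | Baseline | No |
| Two timed samples, one before and one after the dose | The earlier one | Both presumed pre-dose, so the later one as latest | No |

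In the third row, 6.7 falls back on the last value before dosing. This is consistent with SAP 6.6, which fills missing pre-dose Visit 1 laboratory data from preceding visits. In the third and fourth rows, 7.8.2 also departs from its own opening definition.

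**What a conflict would do to the tables.** Two hypothetical patients:

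- Pre-dose grade 1, post-dose Day 1 grade 2, nothing worse later. Under 6.7 the baseline is grade 1, the rise is 2 − 1 = 1 grade, and the patient is flagged. Under 7.8.2 the baseline is grade 2, the rise is 2 − 2 = 0, and the patient is not flagged.
- Pre-dose grade 2, post-dose Day 1 grade 1, later worst value grade 2. Under 6.7 the rise is 2 − 2 = 0 and there is no flag. Under 7.8.2 the rise is 2 − 1 = 1 and the patient is flagged.

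The error can therefore go either way. It arises only for parameters measured in the post-dose sample, and these categorical tables change only where the CTCAE grade differs between the two candidate baselines.

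**Which outputs use this baseline.**

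- They do: the baseline-to-worst and baseline-to-last CTCAE transitions, and the possible clinically significant abnormality table (SAP 7.8.2).
- The worst on-treatment grade is not measured against baseline. SAP 7.8.2 includes the baseline value in the on-treatment period, so a post-dose Day 1 value counts under either rule.
- The tumor lysis screen (SAP 7.8.1) has its own relative baseline for each BI 836858 infusion.
- The DILI and potential Hy's law rules and the eDISH plot (SAP 7.8.2) use multiples of the upper limit of normal.
- MTD and DLT (SAP 5.1 and 7.4) do not use a laboratory baseline.

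**How often the conflict can arise.** It needs both a post-dose sample on the day of first dosing and a recorded sample time.

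- Day 1 of Cycle 1 is decitabine only; BI 836858 starts on Day 8, or Day 9 at the latest (protocol 4.1.3).
- The Flow Chart shows one Day 1 mark each for hematology and biochemistry, and no post-dose safety sample that day is visible.
- The explicit instruction to enter sample date and time in the eCRF stands in the tumor lysis monitoring text of protocol 5.3.6.1. The visible text has no such instruction for routine Day 1 samples.
- Protocol Table 1, which holds the tumor lysis sampling times, is not in the available text.

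The synopsis gives 16 + 33 = 49 patients entered in Phase I. The number affected therefore lies between 0 and 49, and the documents do not narrow that range.

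**The case against.** The strongest reply is that 7.8.2 is only a shortened restatement of 6.7. It opens with the right definition and then presumes that same-day samples followed the protocol, which asks for sampling before dosing. The general paragraph of 6.7 makes the same presumption and names laboratory tests. On this view the sections differ in detail, not in intent. With no post-dose Day 1 sample visible in the schedule, both could give identical tables. SAP 7.8.2 also rests on the sponsor's laboratory-data guideline (SAP reference 9), which may settle the matter and cannot be checked here.

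Much of this stands. A reader might infer that 7.8.2 chooses post-dose values as baseline. The text does not support that: it presumes compliance, and a post-dose value gets in only if one was drawn. A reader might also infer that a first-day worsening would be hidden. That goes too far, because the value would still count towards the worst on-treatment grade. Nor would every laboratory parameter be affected.

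The inconsistency itself remains. The protocol's pre-dose instruction allows exceptions, and the time check in 6.7 deals with samples taken out of order. Section 7.8.2 omits that check in the place where the laboratory tables are specified. The general presumption in 6.7 does not rescue it, because that paragraph yields to the laboratory-specific rule below it.

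**Conclusion.** The two sections contradict each other for one kind of value: a laboratory sample on the day of first dosing with a recorded time after the dose. For every other same-day sample they agree. As written, 7.8.2 would let such a value serve as baseline against its own definition.

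The consequence is small and possibly nil. It is limited to two descriptive transition tables and one descriptive abnormality table. The worst on-treatment grade keeps the post-dose value under both rules, and the tumor lysis screen, the liver-injury and Hy's law rules and the MTD/DLT endpoints do not use this baseline. That the SAP text conflicts is certain. That any patient's result changes is not shown: it would take a timed post-dose sample on Cycle 1 Day 1, and a difference in CTCAE grade for these tables to move. A reader might conclude that two programmers would necessarily produce different tables, but the documents support that only if such samples exist.

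This assumes that first dosing means the first dose of either drug. SAP section 3 defines trial medication, the term in 6.7, as either of the two drugs. It does not define the terms study medication and study drug used in 7.8.2. Protocol 7.3 uses study medication for either drug, so the wording need not be read as a second conflict, but it should be aligned.

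**What to change.** In SAP 7.8.2, delete the sentence on same-day laboratory values and refer to the laboratory baseline rule in 6.7. State once, in 6.7, that a same-day sample is assumed to be pre-dose only when no sample time was recorded. Use the term trial medication in 7.8.2, as in 6.7.

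This costs one sentence and a cross-reference. It needs no new data, and the rule to keep is already in the SAP. A listing of laboratory samples timed after the first dose on Cycle 1 Day 1 would show whether any patient is affected.

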Medical and scientific judgement should be exercised in deciding whether other situations should be considered serious reactions, such as important medical events that might not be immediately life threatening or result in death or hospitalisation but might jeopardise the patient or might require intervention to prevent one of the other outcomes listed above. Examples of such events are intensive treatment in an emergency room or at home for allergic bronchospasm, blood dyscrasias or convulsions that do not result in hospitalisation or development of dependency or abuse. Any suspected transmission via a medicinal product of an infectious agent is also considered a serious adverse reaction.

AEs considered “Always Serious”

In accordance with the European Medicines Agency initiative on Important Medical Events, Boehringer Ingelheim has set up a list of AEs, which by their nature, can always be considered to be “serious” even though they may not have met the criteria of an SAE as given above.

The latest list of “Always Serious AEs” can be found in the RDC portal. A copy of the latest list of “Always Serious AEs” will be provided to the Investigators/sites upon request. These events should always be reported as SAEs as described in [Section 5.3.9](#).

Adverse events of special interest (AESIs)

The term AESI relates to any specific AE that has been identified at the project level as being of particular concern for prospective safety monitoring and safety assessment within this trial, e.g. the potential for AEs based on knowledge from other compounds in the same class. AESI need to be reported to the Sponsor’s Pharmacovigilance Department within the same timeframe that applies to SAE, see [Section 5.3.9](#).

The following are considered as protocol-specified AESIs:

- Infusion-related reactions (CTCAE grade 3 or higher)
- Tumor Lysis Syndrome (any CTCAE grade)
- Any event that qualifies for DLT
- Drug Induced Liver Injury (DILI)

A hepatic injury (DILI) is defined by the following alterations of hepatic laboratory parameters:

- an elevation of AST and/or ALT \geq 3-fold ULN combined with an elevation of total bilirubin \geq 2-fold ULN measured in the same blood draw sample, and/or
- marked peak aminotransferase (ALT, and/or AST) elevations \geq 10-fold ULN

These laboratory findings constitute a hepatic injury alert and the patients showing these laboratory abnormalities need to be followed up according to the “DILI checklist” provided in the ISF.

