As defined in the CTP a hepatic injury (DILI) is defined by the following alterations of hepatic laboratory parameters:

- an elevation of AST and/or ALT >3 fold ULN combined with an elevation of total bilirubin >2 fold ULN measured in the same blood draw sample, and/or
- marked peak aminotransferase (ALT, and/or AST) elevations ≥ 10 fold ULN

Potential Hepatic enzyme elevations (potential Hy's law cases): These are defined as those cases where a combination of all of the following events occurred: any on-treatment value of ALT and/or AST > 3 ULN with total bilirubin ≥ 2 ULN and ALKP < 2 ULN. The events can occur in any order, but must occur within 14 days of the previous event, i.e. the second event must occur within 14 days of the first event, and the third event must occur within 14 days of the second event, etc. Subjects with missing laboratory values for liver enzymes will be excluded from these analyses.

In addition, eDISH plot will be plotted to display the maximum on-treatment AST/ALT and maximum bilirubin in terms of ULN.

Neutrophil and platelet counts of each patients will be plotted in log scale graphs.

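### The SAP presents its hepatic injury (DILI) definition as the protocol's, but replaces at least 3-fold and at least 2-fold ULN by strictly above, so a laboratory-derived flag can drop cases exactly on a limit

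*SAP*

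**What the plan says.** Protocol 5.3.8.1 lists DILI among the adverse events of special interest (AESIs) and gives two laboratory criteria, either of which suffices. The first is "an elevation of AST and/or ALT \geq 3-fold ULN combined with an elevation of total bilirubin \geq 2-fold ULN" (the sign written as \geq means at least), measured in the same blood draw. The second is an AST or ALT of 10-fold ULN or more. On meeting either, the protocol says: "These laboratory findings constitute a hepatic injury alert".

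SAP 7.8.2 introduces its own statement with "As defined in the CTP a hepatic injury (DILI) is defined by the following alterations of hepatic laboratory parameters". Its first criterion is "an elevation of AST and/or ALT >3 fold ULN combined with an elevation of total bilirubin >2 fold ULN", again in the same draw. Its second is "marked peak aminotransferase (ALT, and/or AST) elevations ≥ 10 fold ULN", which agrees with the protocol.

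Two other parts of the SAP bear on this. Section 7.8.1 takes the AESIs, DILI included, from protocol 5.3.8.1 and says that AESIs will be tabulated. Section 4, which records changes to the planned analysis, mentions only the cancellation of Phase II.

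**The concern.** The SAP attributes to the protocol a rule that the protocol does not contain. A programmer who works from SAP 7.8.2 would code strict inequalities. One who follows the reference in SAP 7.8.1 back to the protocol would code non-strict ones. The two could classify the same patient differently on a named safety event.

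Investigators report DILI under the protocol limits. A patient exactly on a limit would therefore be a reported AESI but would fail a flag derived from the laboratory data under SAP 7.8.2, and the two sources would disagree with no explanation on file.

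**Working it through.** No figure in the plan needs reproducing; the check compares two definitions.

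**Inputs.** For one blood draw, let A be the larger of AST and ALT, each divided by its own ULN, and let B be total bilirubin divided by its ULN.

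- Protocol 5.3.8.1: (A ≥ 3 and B ≥ 2) or A ≥ 10
- SAP 7.8.2: (A > 3 and B > 2) or A ≥ 10

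**Every possible result, sorted by region.**

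| Result in one draw | Protocol | SAP |
|---|---|---|
| A < 3, any B | no | no |
| 3 ≤ A < 10, B < 2 | no | no |
| A = 3, B ≥ 2 | **yes** | **no** |
| 3 < A < 10, B = 2 | **yes** | **no** |
| 3 < A < 10, B > 2 | yes | yes |
| A ≥ 10, any B | yes | yes |

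The regions cover all values of A and B. The definitions differ in two of them, and in both the protocol says yes and the SAP says no. No region runs the other way, so the SAP set is a strict subset of the protocol set. Any misclassification is therefore a lost case.

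**Can equality occur?** The documents give no ULNs, so these values are assumptions for illustration. With an ALT ULN of 40 U/L, 3 x 40 = 120 U/L is a result a laboratory can report. With a bilirubin ULN of 1.2 mg/dL, 2 x 1.2 = 2.4 mg/dL is too. The choice of ULN is not critical: three times any whole-number ULN is a whole number, and twice any one-decimal ULN has at most one decimal. Exact equality is possible, but it is a single value on each scale.

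**From draw to patient.** A patient is lost only if every draw that meets the protocol rule falls in one of the two bold regions. One draw that clears both limits, or reaches 10-fold, keeps the patient in.

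**Could the sign be a reading error?** This is unlikely. The same SAP section prints the at-least sign correctly for the 10-fold limit and again for bilirubin in the potential Hy's law rule.

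**The case against.** The strongest reply is that little depends on these signs. The AESI table already rests on the protocol limits through SAP 7.8.1, and the hepatic alert and its follow-up are protocol procedures that the SAP does not alter. SAP 7.8.2 names no table of laboratory-derived DILI cases. The eDISH plot shows maximum AST/ALT and maximum bilirubin in multiples of ULN, so a patient on a limit stays visible under either sign. The analyses are descriptive, without formal tests (protocol 7.2), and development has stopped. All of this stands and limits the size of the point. It does not make the SAP's definition the protocol's.

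A reader might infer three stronger things that the documents do not support.

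- **That DILI cases drop out of the AESI analysis.** They do not, because SAP 7.8.1 ties that analysis to protocol 5.3.8.1.
- **That a material share of patients is affected.** With 16 + 33 = 49 patients in Phase I (protocol synopsis), one patient would be 1/49 = 2.0%. That figure presupposes a case exactly on a limit, and neither document gives a case count.
- **That the SAP contradicts itself**, because its Hy's law rule reads "any on-treatment value of ALT and/or AST > 3 ULN with total bilirubin ≥ 2 ULN and ALKP < 2 ULN" and so accepts bilirubin at exactly 2 x ULN. That rule is a separate construct: it adds an alkaline phosphatase condition and links events by 14-day windows instead of a single draw. The protocol text available gives no Hy's law rule for it to match, so its limits may differ from those for DILI.

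**Conclusion.** The mismatch is real and undeclared. SAP 7.8.2 cites the protocol's DILI definition and then states a narrower one. The error has one direction, since protocol-defined cases can be lost and none gained, but it is confined to results exactly at 3 x ULN for AST/ALT or exactly at 2 x ULN for bilirubin with AST/ALT below 10 x ULN. The practical effect is small: such results should be rare, and the AESI tabulation is not affected.

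The remaining exposure is any DILI flag or listing programmed from SAP 7.8.2, which could disagree with the investigator-reported AESIs. This rests on the SAP meaning what it says when it refers to the protocol. If a narrower rule was intended, the fault is that section 4 does not declare it.

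**What to change.** In the DILI definition in SAP 7.8.2, change the first criterion to AST and/or ALT ≥ 3-fold ULN combined with total bilirubin ≥ 2-fold ULN, so that it matches the protocol section it cites. Leave the 10-fold criterion and the potential Hy's law rule unchanged. Check that any program deriving a DILI flag uses the same signs.

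The cost is two symbols in the SAP and a program check. Data collection and the protocol are untouched.

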5.3.6 Safety laboratory parameters

5.3.6.1 General safety laboratory parameters

Blood samples and urine have to be collected at the time points specified in the [Flow Chart](#). All safety laboratory examinations will be performed at the Investigator's local laboratory and include hematology, biochemistry, coagulation and qualitative urine analysis:

Hematology	Hemoglobin, white blood cell count (WBC) with differential count, platelets
	Reticulocytes have to be measured only at Visit 1 of every second cycle, EOT and EoR visit
Biochemistry	Glucose, sodium, potassium, calcium, inorganic phosphate, creatinine, aspartate amino transferase (AST), alanine amino transferase (ALT), alkaline phosphatase (AP), lactate dehydrogenase, total bilirubin, urea (preferred) or BUN, total protein, albumin, uric acid, C-reactive protein (CRP). Serum immunoglobulin levels (IgG, IgM, IgA) and direct antiglobulin test have to be measured only every other cycle (starting on Day 1 of Cycle 1) and at the EOT visit.
Coagulation	Activated partial thromboplastin time, prothrombin time, international normalized ratio where indicated (e.g. treatment with vitamin K antagonists)
Urine	pH, glucose, erythrocytes, leukocytes, protein, nitrite will be analyzed by dipstick and reported as semiquantitative measurements at screening, completion of Cycle 4 and at EOT visit. In case of pathological findings, further evaluation should be performed and results documented.
Pregnancy test	A serum pregnancy test needs to be obtained at the time points indicated in the Flow Chart in patients of childbearing potential.

Monitoring for laboratory evidence of tumor lysis syndrome

Tumor lysis syndrome (TLS) is characterized by a group of metabolic derangements caused by the massive and abrupt release of cellular components into the blood after rapid lysis of malignant cells, potentially leading to hyperuricemia, hyperkalemia, hyperphosphatemia, hypocalcemia, and uremia ([R10-4517](#)). To allow for early treatment in case TLS develops, vigilant monitoring is mandatory.

Parameters for TLS screening are included in the routine safety labs. Additional blood samples for TLS monitoring have to be obtained at the time points in Cycle 1 indicated in [Table 1](#), further samples may be obtained as clinically indicated. Sampling for TLS in course

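### The SAP's potential Hy's law rule counts ALKP below 2 ULN as a timed event, so it can flag patients whose ALKP was 2 ULN or more at the peak and can join ALT/AST and bilirubin rises up to 28 days apart

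*SAP*

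**What the plan says.** SAP 7.8.2, in the part on hepatic injury, says that a potential Hy's law case exists where "a combination of all of the following events occurred", and gives the components as "any on-treatment value of ALT and/or AST > 3 ULN with total bilirubin ≥ 2 ULN and ALKP < 2 ULN". On timing it says "The events can occur in any order, but must occur within 14 days of the previous event", and spells this out: "the second event must occur within 14 days of the first event, and the third event must occur within 14 days of the second event".

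It sets no limit on the total span or on the interval between the ALT/AST and bilirubin elevations. It does not say that ALKP must be below 2 ULN when either elevation is measured.

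The hepatic injury (DILI) definition just above it works differently. It needs the aminotransferase elevation together with "total bilirubin >2 fold ULN measured in the same blood draw sample, and/or", or a marked aminotransferase peak of at least 10 ULN. Protocol 5.3.8.1 likewise has "2-fold ULN measured in the same blood draw sample, and/or". Neither DILI definition uses ALKP.

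**The concern.** The first two criteria are abnormal findings with a date. ALKP below 2 ULN is not: it covers normal and mildly raised values, and a patient may meet it at many visits. The SAP does not state its purpose, but presumably it is there to set aside cholestatic patterns. To do that it has to describe the patient when ALT/AST and bilirubin are raised. As a timed event it can be met by a sample from another week.

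At stake is whether the flag applies its own third criterion and its own 14-day window. Bilirubin rises unconnected with an ALT/AST rise are foreseeable here: exclusion criterion 10 (protocol 3.3.3) admits patients whose raised bilirubin is attributed to hepatic AML infiltration, Gilbert syndrome or hemolysis. Two programmers could also read the sentence differently and report different counts.

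**Working it through.** **Is ALKP really a timed event?** ALT and/or AST is one criterion. The SAP nevertheless speaks of a third event, and there is a third only if ALKP below 2 ULN is counted. One could take the word joining ALT/AST to bilirubin to mean that they are concurrent, but free ordering and a three-step chain contradict that.

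**The rule as a formula.** Let A be a day with ALT/AST > 3 ULN, B a day with bilirubin ≥ 2 ULN and K a day with ALKP < 2 ULN. Sort the three days as t1 ≤ t2 ≤ t3. The patient is flagged if some choice gives t2 − t1 ≤ 14 and t3 − t2 ≤ 14.

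**The plan's figure.** The only stated figure is 14 days between consecutive events. If A and B alone were timed, the largest A-to-B gap would be 14 days. With K as the middle event it is 14 + 14 = 28 days. Enumerating all day combinations, daily and on weekly draws, also gives a maximum of 28.

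**Sampling.** The protocol Flow Chart has roughly weekly visits (Days 1, 8, 15, 22, 29 from Cycle 2). Protocol 5.3.6.1 puts "alkaline phosphatase (AP), lactate dehydrogenase, total bilirubin", AST and ALT in one biochemistry panel, so a bridging ALKP value will often exist, and so will a same-sample one. SAP 7.8.2 also counts the baseline laboratory value as on-treatment.

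**Constructed patients** (values in multiples of ULN):

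| Pattern | Sorted days and gaps | Printed rule |
|---|---|---|
| Day 1 ALKP 1.1; Day 8 ALT 5, bilirubin 3, ALKP 4 | 1, 8, 8: gaps 7 and 0 | flagged |
| A and B on Day 29; ALKP ≥ 2 on Day 29 only | K on Day 22: gaps 7 and 0 | flagged |
| A and B on Day 29; ALKP ≥ 2 on Days 22, 29, 36 | K on Day 15: gaps 14 and 0 | flagged |
| A and B on Day 29; ALKP ≥ 2 on every draw from Day 15 to Day 43 | nearest K on Day 8: gap 21 | not flagged |
| A on Day 1, B on Day 29, K on Day 15 (Cycle 2 or later) | gaps 14 and 14 | flagged, A to B 28 days |
| A on Day 1, B on Day 29, K only on Day 8 or only on Day 22 | larger gap 21 | not flagged |
| A on Day 8, K on Day 16, B on Day 29 (Cycle 1) | gaps 8 and 13 | flagged, A to B 21 days |
| Same day: ALT 4, bilirubin 2.5, ALKP 1.2 | gaps 0 and 0 | flagged |

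The first three rows show that ALKP at the peak does not decide the flag. A patient with both elevations in one draw escapes only if ALKP is ≥ 2 ULN on every draw within 14 days on either side. The fifth to seventh rows show that intervals beyond 14 days arise only when K falls between A and B, and that the full 28 days needs K exactly 14 days from each.

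**The case against.** The literal reading is hard to dispute; the case against concerns its importance and the remedy.

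- **Importance.** A reader might infer that a main liver-safety result is compromised. The documents do not support this. The protocol-specified liver event is DILI, which has its own definition. The Hy's law flag sits among descriptive laboratory analyses, is no endpoint and drives no MTD decision. Phase I entered 16 + 33 = 49 patients. This stands.
- **Frequency.** A reader might infer that the ALKP criterion excludes almost nobody. No ALKP distribution is given, ALKP raised throughout the window is excluded, and sampling can be sparser than weekly: visits may be skipped during maintenance in CR (protocol 6.2.2), and laboratory tests are not mandatory in cycles above 7 under version 7.0. This stands. The full 28-day example also does not fit nominal Cycle 1 days, where Day 16 replaces Day 15, although 21 days does.
- **Over-inclusion may be intended.** A screen for potential cases may favour sensitivity, and demanding ALKP < 2 ULN in both samples would lose sequential cases. Take ALT 8 with ALKP 1.2 on Day 8, then bilirubin 3 with ALKP 2.1 on Day 15: the printed rule flags this patient, a both-samples rule does not. This bears on the remedy and is met below.
- **Unseen standard.** SAP 7.8.2 bases laboratory analyses on a sponsor standard that is not available here and may specify ALKP timing. It cannot be assumed to override an explicit rule printed in the SAP.
- **Other causes.** Rises due to infection or leukaemic infiltration, within 14 days and with ALKP < 2 ULN, are flagged under any version. That is a causality question which the wording cannot settle.

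**Conclusion.** The rule is wrong as written and should be corrected. Read literally, it (1) flags patients whose ALKP was ≥ 2 ULN at the ALT/AST and bilirubin peak whenever an ALKP value < 2 ULN lies within 14 days, and (2) stretches a 14-day link to as much as 28 days between ALT/AST and bilirubin. Both results follow from the printed words alone.

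The error is towards over-inclusion, in a descriptive flag. The patients above are constructed to show what the rule does; they do not estimate how often it happens, and the documents give no basis for such an estimate. The conclusion assumes that the flag is programmed from the SAP text and that ALKP is drawn with ALT, AST and bilirubin, as the single panel implies.

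**What to change.** Replace the timing sentence in SAP 7.8.2 so that:

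1. the only timed events are ALT/AST > 3 ULN and total bilirubin ≥ 2 ULN, at most 14 days apart in either order;
2. ALKP < 2 ULN is a concurrent condition, read in the sample with the qualifying ALT/AST elevation;
3. one ALT/AST-bilirubin pair that meets both conditions is enough;
4. any patient with both elevations within 14 days who fails only on ALKP is listed separately.

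Applied to the examples: the patients with ALKP ≥ 2 ULN at the peak move to the separate list; the 21-day and 28-day pairs are no longer flagged; the same-day case stays; and the sequential case under the objection stays, because ALKP was 1.2 in its ALT sample and the gap is 15 − 8 = 7 days.

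The cost is a short SAP change and a simpler derivation, with no new data. Fewer patients will be flagged. Those with both elevations remain visible in the eDISH plot, which shows maxima without timing or ALKP. They appear under the DILI definition only if the elevations are in the same draw or ALT/AST is ≥ 10 ULN, so DILI reporting does not catch every patient who drops out. Point 3 also keeps some patients whose ALKP rises after the ALT/AST sample; that is the price of not losing sequential hepatocellular cases.
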